### **7.3. Subject Withdrawal and Replacement**

In addition to the stopping rules described in Section above a subject will be withdrawn by the Investigator or designee from the study and not be allowed to continue with the study if any of the following criteria are fulfilled:

- If discovered that the subject has entered the study in violation of the inclusion/exclusion criteria stated in the protocol;
- Investigator or the Sponsor stops the study, for any reason (e.g., suspension or discontinuation of study drug development).

While subjects are encouraged to complete all study evaluations, they may withdraw from the study at any time and for any reason. Every effort will be made to determine why any subject withdraws from the study prematurely. All subjects who withdraw from the study with an ongoing AE must be followed until the event is resolved or deemed stable. If a subject withdraws prematurely after dosing, all data to be collected prior to discharge from the clinical centre should be collected at the time of premature discontinuation or at the scheduled discharge.

Subject participation may be terminated prior to completing the study and the reason recorded as follows:

1. Adverse event;
2. Protocol violation;
3. Loss to Follow-up;
4. Subject withdrew consent at own request;
5. Other.

A genuine effort must be made to determine the reason(s) why a subject fails to return for the necessary visits or is discontinued from the study. At least 3 attempts of telephone contacts must be documented by the site. In case of failure, the patient is considered lost to follow up.

The subject who will be screen failed for not meeting the inclusion or exclusion criteria or will withdraw the consent during the Screening procedures or before the first IMP administration will be replaced by the next qualifying alternate.

The subject who will be withdrawn for any reason or withdraws from the study after any IMP administration or before completing the study, may be replaced by another qualifying alternate but only in case if total number of subjects in a given study arm who would complete the study would be insufficient and there are no safety concerns.

The subject replacement is defined as recruiting additional patients, but it should be remembered that all randomized patients will be analyzed according to the population set definitions described in this Protocol.

The replacing subject is to follow the same treatment and protocol procedures as the withdrawn one. The replacing alternate subject is to receive the study products under the same conditions as the withdrawn subjects, and they are to undergo the entire protocol procedure.

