## 4. STUDY DESIGN

### 4.1. Overview

This is to be a 12-week, phase II, multicentre, randomised, double blind, efficacy and safety study of CPL409116 in participants with active rheumatoid arthritis who are taking methotrexate but have an inadequate response to this drug.

Approximately 100 male and female subjects are to be enrolled in the study. Eligible subjects are to be randomized into one of the 4 treatment arms determined in points below:

- **25** are to be randomized to the treatment arm with CPL409116 at a dose of 60 mg BID;
- **25** are to be randomized to the treatment arm with CPL409116 at a dose of 120 mg BID;
- **25** to the treatment arm with CPL409116 at a dose of 240 mg BID;
- **25** to the treatment arm with placebo.

Randomisation ratio is to be: 1:1:1:1. This will be the age-stratified randomisation. In all treatment arms investigated product/ placebo is to be administered orally for 12 weeks in a blinded fashion. In order to maintain the blind and minimize bias, all subjects will receive the same number and types of tablets each day of treatment.

Timepoints for CPL409116/ placebo administration are to be determined according to results obtained in the Phase I clinical trial with CPL409116 (PART A and PART B of the study).

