#### **Randomization Codes**

At the end of the Screening, patients will be assigned a randomisation code generated by a randomisation system in the electronic case report form. The randomisation code will consist of four letters. The random coding system is described in a separate document.

Once a randomization code has been allocated to one subject, it may not be assigned to another subject.

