- Collect blood sample for ESR testing, RF, ACPA, CRP\*;
  - \* CRP must be assessed two times at Screening, the first time up to 72h before Day 1/baseline (for evaluation of DAS28-CRP) and the second time within the 72-hour period before Day 1/baseline to use a measurement result for DAS28-CRP evaluation on Day 1/ baseline. If patient's CRP level is below 7 mg/L on Screening visit, it is possible to perform CRP measurement once again within 28 days of Screening period, provided at least 14 days since initial CRP measurement and prior to Day -5 before Baseline;
- Collect blood sample for pregnancy test;
- Collect blood sample for FSH testing (WONCBP only);
- Collect urine sample for urinalysis and urine microscopy;
- Confirmation of proper contraception usage;
- Collect blood samples for HIV Serology, HBsAg, HBcAb, HBsAb, HBV DNA HCVAb and/or HCV RNA;
- Human immunodeficiency virus (HIV) testing is mandatory;
- Collect blood for tuberculosis (QuantiFERON Gold®TM In-Tube) test;
- Collect swab sample for SARS-CoV-2 infection testing (PCR) (72h before Day 1/ baseline) and conduct interview regarding possible SARS-CoV-2 infection;
- Collect urine sample for toxicology tests (presence of drugs in urine), alcohol breath test;
- Perform assessment of tender and swollen joints RA;
- Evaluation of DAS28-CRP

- SAE and AE monitoring.
- Randomisation into one of four arms, as follows: 60 mg BID; 120 mg BID; 240 mg BID; placebo).

**NOTE:** Randomisation will take place at the end of the screening period when it is confirmed by an Investigator that a participant fulfilled all inclusion criteria and none of exclusion criteria available at the time of randomisation (pre-final confirmation). Patients will be randomised at the end of the screening period (1-2 days before Day1/ baseline) in order to generate the randomisation code which is necessary to prepare appropriate number of IMP/ placebo for a patient. Pre- final conformation will take place after the negative result of COVID-19 test is received. The rest of inclusion and exclusion criteria unavailable at Screening will be verified on Day1/ baseline (final conformation). The final conformation will take place before the first dose of IMP/placebo administration on Day1/ baseline.

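### Protocol 7.3 tells a replacement to follow the withdrawn patient's treatment, which does not fit age-stratified randomisation of every patient; separately, SAP 3.5 and Protocol 6.8 disagree on by-arm PK before lock

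*Protocol*

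**What the plan says.** **Replacement.** Protocol 7.3 has two routes. A patient who fails screening, or withdraws consent before the first dose, is replaced as a matter of course. A patient lost after dosing may be replaced, "only in case if total number of subjects in a given study arm who would complete the study would be insufficient", and only without safety concerns. The section then adds: "The replacing subject is to follow the same treatment and protocol procedures as the withdrawn one".

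Two other statements in 7.3 point elsewhere. One reads "The subject replacement is defined as recruiting additional patients, but it should be remembered that all randomized patients will be analyzed". The other says of replacements that "they are to undergo the entire protocol procedure".

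**Allocation.** Protocol 4.1 sets a 1:1:1:1 ratio and says "This will be the age-stratified randomisation". SAP 2.2.2 adds randomly permuted blocks and an age cut-off of 57 years. Under Randomization Codes (Protocol 6.4), "patients will be assigned a randomisation code generated by a randomisation system in the electronic case report form" at the end of Screening, and a code given to one patient may not be given to another. The same section says "The random coding system is described in a separate document". Protocol 9.1 confirms that "Randomisation will take place at the end of the screening period", 1 to 2 days before Day 1, with final eligibility checked on Day 1.

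**PK and PD timing.** Protocol 6.8 breaks the overall code after database lock and for reporting only. SAP 3.5 exempts PK and PD from waiting for lock: they are analysed once every patient has ended treatment. SAP 4.13 summarises PK by dose arm. SAP 2.2.2 sends the complete concentration table to the sponsor's Clinical Department.

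**The concern.** The replacement sentence names treatment separately from protocol procedures, so its natural meaning is the same arm. The arm-level trigger supports that meaning, because topping up a short arm works reliably only if the newcomer is placed there. A patient placed in this way would not come from the permuted-block list, might belong to the other age stratum, and would not clearly meet the FAS and ITT definitions, which cover randomised patients. Counting completers by arm while the trial runs also needs unblinded information. Unblinded pharmacy and monitoring staff exist (Protocol 6.7 and 6.8), but no role is named for this decision, and no number defines an insufficient arm.

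The sentence may also reach patients randomised 1 to 2 days before Day 1 who then fail or withdraw before dosing. Their replacement is not optional.

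On PK, concentrations should separate placebo from active patients. If sponsor staff hold them before lock, decisions that the SAP describes as blinded could be taken with that knowledge available.

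**Working it through.** **1. Replacement wording against allocation wording**

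| Question | If the arm is copied from the withdrawn patient | If the patient is freshly randomised |
|---|---|---|
| Same treatment as the withdrawn patient (7.3) | fits | does not fit, unless treatment only means regimen and schedule |
| Trigger counted by arm (7.3) | fits | fits poorly: the next allocation may go to another arm |
| Additional patients, entire procedure (7.3) | fits poorly: the procedure includes randomisation (9.1) | fits |
| System code for every patient, no re-use (6.4) | needs a new code in a chosen arm | fits |
| 1:1:1:1 blocks within age stratum (4.1; SAP 2.2.2) | does not fit | fits |
| FAS and ITT contain randomised patients (10.2; SAP 3.1) | unclear | fits |

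No single reading satisfies every row, so the passages need to be reconciled.

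**2. How often the optional route could come into question**

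The plan's own figure: 84/(1 - 0.16) = 100 recruited, and 25 x 0.84 = 21 completers per arm. Both reproduce.

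Assumptions not in the documents: dropouts per arm X ~ Bin(25, p), independent, and an arm is short if 25 - X < T. With P the chance that one arm is short, the chance for at least one of four arms is 1 - (1 - P)^4.

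| T (assumed) | P, p = 16% | Any of 4, p = 16% | Expected total shortfall, p = 16% | Any of 4, p = 10% | Any of 4, p = 20% |
|---|---|---|---|---|---|
| 21 | 0.371 | 84% | 2.9 | 34% | 97% |
| 20 | 0.200 | 59% | 1.4 | 13% | 86% |
| 19 | 0.092 | 32% | 0.6 | 4% | 63% |
| 18 | 0.036 | 14% | 0.2 | 1% | 37% |

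A short arm at p = 16% lacks 1.5 to 1.9 patients on average. One replacement would be 1/26 = 3.8% of an arm and two would be 2/27 = 7.4%. The pre-dose route is not quantified, because the documents give no rate for it.

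**3. What is lost if arms are not topped up**

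Unadjusted two-sample t-test, difference 0.8, SD 1.1, two-sided 5%, noncentral t:
- 21 v 21: noncentrality 0.8/(1.1 x sqrt(2/21)) = 2.36, df 40, power 63.3%.
- 18 v 21: noncentrality 0.8/(1.1 x sqrt(1/18 + 1/21)) = 2.26, df 37, power 59.7%.

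The loss is about 4 points. The level is not comparable with the plan's figure of more than 80%, which comes from an ANCOVA simulation; only the difference is used here.

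**4. PK timing**

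Samples per patient: 3 x 9 + 2 + 13 = 42. At 4.5 mL each this is 189 mL, the protocol's own total. The table would cover the planned 25 placebo and 75 active patients. For the last patient, the last PK sample (Day 86) and the last visit (Day 113) are 27 days apart.

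All Week 12 assessments are complete by then. What may still be open:
- Week 16 DAS28-CRP for the last patients, which enters the primary repeated-measures model (SAP 4.11.1).
- Data cleaning.
- Decisions assigned to the data review before unblinding: major deviations and so the PP set (SAP 3.3), targeted adverse events (SAP 4.2.14) and the rescue-medication list (SAP 4.2.16).

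**The case against.** The strongest reply is that a copied allocation could hardly happen in practice. Codes cannot be re-used, and drug can be prepared only once the system has issued a code. Investigators and site staff do not know the withdrawn patient's arm and may break the blind only in an emergency, so a blinded site could not knowingly match it. The disputed words can also be taken to mean the same regimen and visit schedule, which sits well with the remark about additional patients and the entire procedure.

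Much of this stands. A reader might infer that the plan provides for non-random placement of replacements. The documents do not support that: 7.3 contains both readings, and the coding document, which may settle it, is not public. What remains is that an unblinded person or the system itself could still apply the sentence as written, and that the arm-level trigger makes little sense under fresh randomisation.

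A reader might also take 84% as the chance that a replacement occurs. It is only the chance that some arm has fewer than 21 completers, under an assumed threshold and independent dropout. Replacement after dosing is discretionary.

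On PK, one might infer that nothing restricts sponsor access before lock. That is too strong: Protocol 6.8 places the overall code break after lock and exempts no one. SAP 3.5 permits analysis before lock but does not require it, SAP 2.2.2 gives no delivery date for the table, and SAP 4.14 and 4.16, the Safety Management Plan and the Data Management Plan are not visible. What stands is the conflict between the SAP 3.5 exemption, applied to by-arm summaries, and the Protocol 6.8 rule, together with silence in the public text on who at the sponsor may see concentrations.

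**Conclusion.** The replacement sentence should be corrected. As worded it points to placement by rule, and it cannot be squared with system randomisation of every patient, the bar on re-using codes and age-stratified blocks. It is a contradiction in the text, not a demonstrated bypass. Its effect is probably small: no replacement of dosed patients is needed if each arm loses exactly the planned 16%, and a short arm would typically lack one or two patients. The shortfall probabilities are illustrative, because the documents do not say what counts as insufficient. The documents give no basis for a size of bias, and none is claimed. Confidence is medium, since the coding document may already resolve the point.

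The PK point is minor and separate. It does not expose the Week 12 scores. It concerns a timing contradiction that leaves some late data and blinded review decisions open while by-arm results could exist.

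**What to change.** **Protocol 7.3.** Delete the wording on same treatment. State that any added patient, whether replacing someone before or after dosing, receives the next randomisation-system allocation in his or her own age stratum and is analysed as randomised. Base added recruitment on pooled, blinded completer counts against a stated number, or have a named unblinded role decide. If the coding document already says this, cite it.

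Cost: wording only. Completers per arm may be slightly uneven; 18 v 21 instead of 21 v 21 costs about 4 points of power under the simple t-test above.

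**SAP 3.5 and 2.2.2.** Reconcile with Protocol 6.8. Hold the concentration table and by-arm PK and PD results until the data review minutes are signed and the database is locked. Alternatively, restrict them until then to a named unblinded PK group with no part in those decisions. If the Safety or Data Management Plan already does so, a citation is enough.

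Cost: a later PK report, or a simple firewall procedure.

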## **8. STUDY ASSESSMENTS AND PROCEDURES**

For timing of assessments, refer to the Schedule of Assessments Table 1.

### Eligibility Screening

For patient eligibility screening assessments and procedures, please refer to the Schedule of Assessment Table 1.

### Medical History, Demographic and Other Baseline Information:

The medical history comprises:

- General medical history;
- Medication history;
- Reproductive history.

The following demographic information will be recorded:

- Age;
- Race/ethnicity;
- Height, without shoes (cm);
- Body weight, without shoes (kg);
- Body mass index (BMI) (kg/m^2).

Other Baseline characteristics will be recorded as follows:

- History of drug abuse;
- History of alcohol abuse;
- Smoking habits;
- Coffee, tea, and energy drink consumption habits;
- Special diet (vegetarian);
- History of blood or plasma donation.

## **8.1. Safety Variables**

### **Adverse Events**

Adverse event reporting will begin for each subject from the date the informed consent form (ICF) is signed and will continue until the final Follow-up Visit.

#### **Definition of Adverse Event**

Any untoward medical occurrence in a subject administered a medicinal (investigational) product and which does not necessarily have a causal relationship with this treatment. An adverse event (AE) can, therefore, be any unfavorable and unintended sign (including an abnormal laboratory finding), symptom, or disease temporally associated with the use of a medicinal (investigational) product, whether or not related to the medicinal (investigational) product.

Other untoward events occurring in the framework of the study will be recorded as AEs, e.g. those occurring during treatment-free periods (including Screening or post-treatment Follow-up periods), in association with study-related procedures and assessments, or under placebo. For study drugs, lack of efficacy may be an expected potential outcome and should not be reported as an AE unless the event is unusual in some way, e.g., greater in severity.

Concomitant illnesses, which existed prior to entry into the Study, will not be considered AEs unless they worsen during the Treatment Period. Pre-existing conditions will be recorded as part of the subject's medical history.

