#### **The study is to be consisted of 3 phases:**

- A Screening phase of up to 4 weeks,
- A double-blind treatment phase (Day 1 to Day 85/86; 12 weeks) with two doses of IMP administration per day (except Day 85 when patients are to administer only one dose of IMP in the morning and except Day 86 without administration of CPL409116, when the last sample of blood will be collected for PK analysis in the morning).

- A 4 weeks post-treatment follow-up phase up to Week 16 (Day 113). Patients are to come to a study centre two times after the last dose of IMP. According to the schedule assessment in the follow-up period are planned two ambulatory visits and phone calls from clinical centres: Week 14 and 16 (Day 99 and 113 respectively)- an ambulatory visit; Week 13 and 15 (Day 92 and 106 respectively)- phone call from a clinical centre. The end of the study is planned at Week 16 (Day 113).

[figure not shown]

Fig. 3. Overview of the study design.

In the **Screening Period**, patients are to undergo screening assessments from Day -28 to Day 0. Rolling admission is to be employed in this study. Patients that fulfil all the inclusion criteria and none of the exclusion criteria are to will be considered eligible for this study. Subjects must complete all screening procedures and assessments and have test results available prior to the Baseline visit (Visit 2). Clinical centres must fulfil the following steps of the screening period:

- Informed Consent: written informed consent must be obtained prior to performance of any protocol-specific procedures;
- Review of inclusion/ exclusion criteria: all the inclusion criteria and none of the exclusion criteria must be fulfilled;
- Overview of the subject's demographics, RA history and prior RA medication history (start dates and stop dates with reason for discontinuation, dosage, indication);
- Review of Participant's Medical History, including comorbidities, concomitant (non-RA) medications and previous vaccination (influenza, pneumococcus, herpes zoster, SARS-CoV-2);

- Information about history of alcohol and drug abuse;
- Height and weight measurement;
- Vital signs measurement: sitting blood pressure, pulse, temperature;

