#### 4.4. Study Duration

The duration of participation for each patient will be approximately up to 20 weeks. The estimated study duration includes:

- The Screening Period: up to 28 days
- Treatment period: Day 1 to 85/86 days
- Follow-up period: patients are to come to the study centre two times after the last dose of IMP: at Week 14 and Week 16 (Day 99 and Day 113 respectively). On Day 92 and Day 106 the call from the study unit will be made. End of the Study will take place on Day 113, Week 16.

For the entire study, end of the study is defined as the last visit of the last subject for any protocol related activity (last subject, last visit- LSLV).

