#### **Definition of Serious Adverse Event**

A serious adverse event (SAE) is defined as any adverse event, occurring at any dose and regardless of causality that:

- Results in death;

- Is life-threatening; this means that the subject was at risk of death at the time of the event; it does not mean that the event hypothetically might have caused death if it were more severe;
- Requires inpatient hospitalization or prolongation in existing hospitalization. Hospitalization admissions and/or surgical operations scheduled to occur during the study period, but planned prior to study entry are not considered AEs if the illness or disease existed before the patient was enrolled in the trial, provided that it did not deteriorate in an unexpected manner during the trial (e.g. surgery performed earlier than planned);
- Results in persistent or significant disability/incapacity. Disability is defined as substantial disruption of the ability to conduct normal life functions;
- Is a congenital anomaly/birth defect;
- Is another important medical event (see below).

Important medical events that do not result in death, are not life-threatening or do not require hospitalization may be considered SAEs when, based on appropriate medical judgment, they may jeopardize the subject and may require medical or surgical intervention to prevent one of the outcomes listed above in definition of SAEs. Examples of such medical events include allergic bronchospasm requiring intensive treatment in an emergency room or in a physician's office, blood dyscrasias or seizures that do not result in in-patient hospitalization, and the development of drug dependency or drug abuse.

A distinction should be drawn between serious and severe AEs. Severity is a measure of intensity whereas seriousness is defined by the criteria above. For example, a mild degree of gastrointestinal bleeding requiring an overnight hospitalization for monitoring purposes would be considered an SAE but is not necessarily severe. Similarly, an AE that is severe in intensity is not necessarily an SAE. For example, alopecia may be assessed as severe in intensity but would not be considered a SAE.

Medical and scientific judgment should be exercised in deciding if an AE is serious and if expedited reporting is appropriate.

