2.1.2. Secondary endpoints

Clinical Efficacy:

- Proportion of subjects with DAS28-CRP remission at Weeks 4; 8; 12 and 16.
- American College of Rheumatology (ACR)20, ACR 50, ACR 70, and ACR 90 responder rates (Weeks 4, 8 and 12).
- Change from Baseline in the Tender/Painful and Swollen Joint Count (Weeks 4, 8 and 12).
- Change from Baseline in the Physician's Global Assessment (PhGA) of Arthritis (Weeks 4, 8 and 12).

Patient Reported Outcome:

- Change from baseline in the Patient's Assessment of Arthritis Pain (PAAP) VAS and Patient Global Assessment of Arthritis (PtGA, VAS) at Week 4, 8, and 12.
- Change from baseline in the Health Assessment Questionnaire – Disability Index (HAQ-DI) at Week 4, 8, and 12.
- Change from baseline in the SF-36 RAND 8 Domain scores and Physical Component Score (PCS) and Mental component score (MCS) at Week 12.
- Change from baseline in the Functional Assessment of Chronic Illness Therapy Fatigue (FACIT-F) total score at Week 12.

Safety:

Safety and tolerability of CPL409116: vital signs (blood pressure (BP), pulse and temperature), laboratory tests, Adverse Events (AEs) and Serious Adverse Events (SAEs), 12-lead electrocardiogram (ECG):

- Incidence and severity of adverse events, serious adverse events, and withdrawals due to adverse events (Baseline through Week 16).
- Incidence of abnormality in clinical chemistry parameters (Baseline through Week 16).
- Incidence of abnormality in haematological parameters (Baseline through Week 16).
- Change from baseline in blood pressure measurement (Baseline through Week 16).
- Change from baseline in pulse rate measurement (Baseline through Week 16).
- Change from baseline in temperature measurement (Baseline through Week 16).
- Incidences of targeted medical adverse events (Baseline through Week 16).

Pharmacokinetics:

- CPL409116 and metabolite M3 pharmacokinetic variables: $AUC_{(0-6h)}$, C_{max} , T_{max} , $T_{1/2}$ (if possible) and K_{el} (if possible) determined on Day 1, 8, 57 and 85.
- CPL409116 pharmacokinetic variables: C_{0h} , $C_{2.5h}$ determined on Day 29.

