4.12.1. Adverse events analysis

Any undesirable signs, symptoms or medical conditions occurring or worsening of pre-existing conditions between signing informed consent and the first administration study medication are considered as pre-treatment AEs. Undesirable signs, symptoms or medical conditions or worsening of pre-existing conditions occurring after the first administration of study medication are considered as treatment emergent adverse events (TEAEs).

A TEAE will be analyzed as related to study medication (i.e. as adverse drug reaction, ADR) if the relationship to study treatment was documented as 'unlikely', 'possible', 'probable', or 'definite' or if the relationship to study treatment is missing.

An overview table presenting the incidence of the following AE categories will be presented. Percentage of patients in each category will be compared between treatments as a difference in proportions between treatments including a 95% CI based on the Agresti – Caffo method (2000):

- All AEs
- Pre-treatment AEs
- Serious AEs (SAEs) (including pre-treatment SAEs)
- Treatment emergent AEs (TEAEs)
- Treatment emergent SAEs (TESAEs)
- Severe TEAEs
- Related TEAEs
- Related severe TEAEs
- TEAEs leading to reduction of dose
- TEAEs leading to interruption of dose
- TEAEs leading to permanent discontinuation (i.e. withdrawal) of study medication
- Related TEAEs leading to permanent discontinuation of study medication
- AEs leading to death (i.e. outcome of AE is fatal)
- TEAEs leading to death
- Related TEAEs leading to death
- Targeted medical adverse events

Targeted medical adverse events are defined in section 4.2.14.

All treatment emergent AEs (TEAEs) and all serious TEAEs will be tabulated by MedDRA System Organ Class (SOC) and preferred term (PT) presenting the number and percentage of patients reporting the AE and the number of AEs reported. Additional tables will distinguish the events by whether the AE was related to study medication and by maximum severity.

All AEs documented in the eCRF will be listed by patient. Data listings will include patient ID, treatment group, verbatim term, preferred term, system organ class, start and stop date and relative day of the AE, severity, medications (yes/no), seriousness, action taken with study medication, relationship to study medication, and outcome will be provided. TEAEs will be

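### Protocol 8.1 limits worsening of a pre-existing illness to the Treatment Period, which is narrower than the protocol's reporting window, the Week 16 safety endpoint and the SAP's definitions

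*Protocol*

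**What the plan says.** The rule is in protocol 8.1, Definition of Adverse Event: "Concomitant illnesses, which existed prior to entry into the Study, will not be considered AEs unless they worsen during the Treatment Period". Pre-existing conditions go into the medical history instead.

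The capitalised period has a defined end. Section 4.4 gives "Treatment period: Day 1 to 85/86 days", section 9.2 closes the treatment period at the Day 86 discharge, and section 4.1 describes what follows as a separate phase: "A 4 weeks post-treatment follow-up phase up to Week 16 (Day 113").

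Four other places set a wider window:

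- Protocol 8.1, Adverse Events: reporting starts on the date the consent form "is signed and will continue until the final Follow-up Visit". The subsections on recording AEs and on reporting SAEs use the same span.
- Protocol 8.1, Definition of Serious Adverse Event: "A serious adverse event (SAE) is defined as any adverse event, occurring at any dose and regardless of causality that" meets one of the listed seriousness criteria. An SAE is therefore a subset of AEs.
- Protocol synopsis and SAP 2.1.2: the safety endpoint is "Incidence and severity of adverse events, serious adverse events, and withdrawals due to adverse events (Baseline through Week 16").
- SAP 4.12.1: "worsening of pre-existing conditions occurring after the first administration of study medication are considered as treatment emergent adverse events". The sentence before it treats worsening between consent and first dose as a pre-treatment AE. Neither sentence stops at Day 86.

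**The concern.** The recording rule for one class of event covers a shorter window than the endpoint and the analysis that depend on it. The SAP can tabulate only what sites enter. If a site follows the sentence in 8.1 to the letter, a comorbidity that worsens on, say, Day 100 produces no AE record, and no SAP derivation can restore it. Because seriousness is defined on top of AE status, an unplanned admission for that worsening could also, on the same literal reading, fall outside the 24-hour notification to the sponsor.

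What is at stake is completeness and consistency of the AE and SAE counts for worsening of pre-existing disease, in completers as well as in patients who withdraw. In a multicentre trial, SAP 4.12.1 compares proportions between arms with confidence intervals. Sites that read the rule differently add noise to those comparisons. An omission cannot be repaired after the data are collected.

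**Working it through.** **Length of the uncovered stretch after treatment.** The inputs are the end of the Treatment Period (Day 85 or Day 86, protocol 4.4) and the end of study (Day 113, protocol 4.1).

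- From Day 85: 113 − 85 = 28 days; 28 / 7 = 4.0 weeks. This reproduces the protocol's own four-week follow-up.
- From Day 86: 113 − 86 = 27 days; 27 / 7 = 3.9 weeks.
- Share of the Day 1 to Day 113 window: 28 / 113 = 24.8%, or 27 / 113 = 23.9%.

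**Stretch before treatment.** Consent to Day 1 is up to 28 days (screening, protocol 4.4). It lies before Baseline, so it does not touch the Week 16 endpoint. It does touch the SAP's pre-treatment AE category, and the all-AE and SAE categories that include pre-treatment events.

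**How each rule treats a pre-existing illness that worsens:**

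| Rule | Consent to Day 1 | Day 1 to Day 85/86 | After that, to Day 113 |
|---|---|---|---|
| Protocol 8.1, sentence on concomitant illness | not an AE | AE | not an AE |
| Protocol 8.1, AE and SAE reporting window | inside | inside | inside |
| Safety endpoint (synopsis; SAP 2.1.2) | outside | inside | inside |
| SAP 4.12.1 | pre-treatment AE | TEAE | TEAE |

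The first row disagrees with the reporting window and with the SAP in both outer columns, and with the endpoint in the last column.

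**Knock-on to SAEs.** The SAE definition begins from an adverse event. If the first row excludes an event as an AE, the literal wording also excludes it as an SAE, whatever its seriousness.

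**Number of events affected.** Neither document gives a rate at which comorbidities worsen over four weeks, or any basis for the share of such events that sites would leave out. The number lost therefore cannot be computed.

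**The case against.** The strongest reply is that 8.1 should not be read one sentence at a time. Three other protocol provisions lean towards recording:

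- The paragraph just before the rule says that other untoward events in the study framework are recorded as AEs, and names screening and post-treatment follow-up. It does not restrict this to new conditions.
- The SAE definition exempts admissions planned before entry only if the disease did not deteriorate unexpectedly over the trial as a whole.
- Section 8.2 makes a clinically significant laboratory abnormality at a Follow-up Visit an AE, with no exception for pre-existing disease.

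Sites also ask about AEs at every follow-up visit and call. This much stands: a reader might infer that follow-up worsening is definitely neither an AE nor an SAE, and the protocol as a whole does not support anything so absolute. But none of the three removes the exception. The first is a general rule followed directly by a specific one, the second covers only pre-planned admissions, and the third covers only laboratory findings.

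A reader might also infer that harm appearing after the drug is stopped would go unseen. The documents do not support that. No readable passage describes a rebound effect in patients. Vital signs and laboratory values at Days 99 and 113, and ECG at Day 113, are collected and summarised whatever their AE status. A new infection or other new event in follow-up is an AE on any reading.

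Finally, the rule is the same in all blinded arms and protocol 10.7 makes the safety analysis descriptive, so no bias between arms has been shown. That also stands.

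**Conclusion.** The inconsistency is real and should be corrected. The sentence in 8.1 is narrower than the protocol's own reporting window, the safety endpoint and SAP 4.12.1. On its literal wording, worsening of a pre-existing illness before Day 1 or after Day 85/86 may go unrecorded as an AE, and therefore as an SAE. Because neighbouring provisions point the other way, the supportable conclusion is that sites may record the same event differently, not that all such events are lost.

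The size that can be stated is the exposed time: 27 to 28 of 113 days, about 24% to 25% of the Baseline-to-Week-16 window, plus up to 28 days of screening that affect only the tables counting pre-treatment events. A reader might want a count of missing events per arm. That would need an assumed worsening rate and an assumed share left out, and the documents supply neither.

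The conclusion rests on reading the Treatment Period as section 4.4 defines it. Section 4.5 loosely ties completion of the treatment phase to Day 113, but it concerns completion status and does not fit sections 4.1, 4.4 and 9.2. Nothing suggests that the sponsor meant to leave out follow-up worsening; the wider windows elsewhere suggest the opposite. This is a wording fault with a bounded effect.

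**What to change.** In protocol 8.1, Definition of Adverse Event, replace the closing phrase about the Treatment Period so that a pre-existing illness counts as an AE if it worsens at any time from signing of the ICF to the final Follow-up Visit. Send sites a short note saying so. This brings the definition into line with the AE and SAE reporting windows in 8.1, the safety endpoint and SAP 4.12.1. It also closes the gap before Day 1.

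It changes what is recorded, not how patients are managed. No SAP change is needed. The cost is one phrase in an amendment, the site note, and slightly more AE records.
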